4.11. Outcome of Interest

4.11.1. Primary clinical outcome and definition of treatment success

- Primary clinical outcome will be the Pain Self-Efficacy Questionnaire (PSEQ) score (Nicholas, 1989).
 - Patients will be asked to rate how confident they are at the time of examination despite the presence of their pain in performing the following activities, listed by selecting a number on a 7 point scale where 0 equals “not at all confident” and 6 equals “completely confident”:
 - I can enjoy things, despite the pain.

- I can do most of the household chores (e.g. tidying-up, washing dishes, etc.), despite the pain.
- I can socialize with my friends or family members as often as I used to do, despite the pain.
- I can cope with my pain in most situations.
- I can do some form of work, despite the pain (“work” includes housework, paid and unpaid work).
- I can still do many of the things I enjoy doing, such as hobbies or leisure activity, despite the pain.
- I can cope with my pain without additional medication (next to rESWT plus C-E drugs, rESWT alone or C-E drugs alone, respectively).
- I can still accomplish most of my goals in life, despite the pain.
- I can live a normal lifestyle, despite the pain.
- I can gradually become more active, despite the pain.
- Scores on the PSEQ may range from 0 to 60, with higher scores indicating stronger self-efficacy beliefs.
- A point score change of 11 points for the PSEQ score corresponds to the minimal clinically important difference (MCID), defined as the smallest difference that patients and clinicians perceive to be worthwhile when treating chronic non-specific low back pain (Maughan and Lewis, 2010).
- According to Maughan and Lewis (2010) the PSEQ score is responsive to clinically important change over time.
- The PSEQ score will be collected at baseline and at all follow-up examinations, i.e., two weeks, four weeks, 12 weeks and 24 weeks after baseline.
- In the present study treatment success is defined as individual improvement of the PSEQ score by more than 20 points at 12 weeks after baseline.

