4.6. Groups and treatments

Patients in the rESWT plus C-E drugs group will receive the below:

- Celecoxib (1 × 200 mg per day for moderate pain [NRS 4-6; c.f. Section 4.11.2 below] or 2 × 200 mg per day [NRS 7-10]) for four weeks.
- Eperisine (3 × 50 mg per day) for four weeks.
- Four rESWT sessions with the Swiss Dolorclast and the EvoBlue handpiece, as follows:
 - One rESWT session per week.

- 4 × 1000 rESWs per session (1000 rESWs each applied to the left and the right paravertebrate muscles above L3 to S1 using the 36-mm applicator, plus 1000 rESWs each applied to the left and the right sacroiliacal joint using the 15-mm convex applicator, in prone position of the patient).
- rESWs applied at 15 Hz
- Air pressure of the Swiss DolorClast (and, thus, the energy flux density of the applied rESWs) gradually increased during the first 200 rESWs each until the maximum dyscomfort the patient can tolerate will be reached, followed by 800 rESWs at this air pressure / energy flux density.
- No application of local anaesthetics (Rompe et al., 2005; Schmitz et al., 2013; 2015).

Patients in the rESWT group will receive the below:

- Four rESWT sessions with the Swiss Dolorclast and the EvoBlue handpiece as described above for the *rESWT plus C-E drugs* group.

Patients in the C-E drugs group will receive the below:

- Celecoxib and Eperisome as described above for the *rESWT plus C-E drugs* group.

In addition, all patients will be advised to perform simplified, safe core stability training and flexion relaxation training at home, which is mainly based on the contraction of the lumbar muscles, under the guidance of a unified rehabilitation training video (two training sessions per week; each training session lasting for approximately 20 minutes; training for 24 weeks).

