4.12. Blinding of therapists and assessors

- Therapists applying the treatments will not be blinded. This will be done because even when using coded “active” and “placebo” handpieces in a study on ESWT, blinding of ESWT therapists can only be achieved when another person prepares the device before rESWT or sham treatment. This, however, is almost impracticable and has not been done in any of the more than 100 studies on rESWT and fESWT listed in the PEDro database (Schmitz et al., 2015). The solution to this issue is a strict, standardized way of interaction between the ESWT therapist and the patients, irrespective of treatment allocation (as mentioned in a study by Buchbinder et al., 2002). This approach will also be applied in the proposed study.
- All assessments before the first treatment (baseline) and during the follow-up period will be performed by assessors blind to the intervention.

5. Follow-up and statistical analysis

- Follow-up will be the same for all study patients.
- The design of the proposed study guarantees that there will be full compliance with the allocated treatment and, thus, no contamination of one group.
- The patient's age, gender, body mass index, job occupation and duration of non-specific low back pain are potential confounding factors when treating chronic non-specific low back pain with rESWT. Normal distribution of these data will be tested using the D'Agostino-Pearson omnibus test. In case of passing the normality test we will report mean and standard error of the mean of these variables; otherwise we will report inter-quartile ranges of these variables. Comparison between groups will be performed with ANOVA followed by Bonferroni post tests for pairwise comparisons in case of passing the normality test, or the nonparametric Kruskal-Wallis test followed by Dunns tests for pairwise comparisons in case of not passing the initial normality test.
- As outlined in Section "Primary clinical outcome and definition of treatment success" above, the primary clinical outcome will be the PSEQ score at 12 weeks after baseline. Treatment success (i.e., number of patients with individual improvement of PSEQ score by more than 20% at 12 weeks after baseline) will be tested with Fisher's exact test.

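### PSEQ item 7 defines additional medication relative to the allocated treatment, so one of the ten primary-outcome items is not strictly comparable between rESWT alone and the two C-E arms

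*Combined protocol and SAP*

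**What the plan says.** Section 4.11.1 makes the PSEQ the primary clinical outcome. It is self-rated: "Patients will be asked to rate how confident they are at the time of examination". Ten statements follow, each scored 0 to 6, and "Scores on the PSEQ may range from 0 to 60, with higher scores indicating stronger self-efficacy beliefs". The seventh is "I can cope with my pain without additional medication (next to rESWT plus C-E drugs, rESWT alone or C-E drugs alone, respectively".

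On timing, the same section says "The PSEQ score will be collected at baseline and at all follow-up examinations", that is, at weeks 2, 4, 12 and 24. It adds that "treatment success is defined as individual improvement of the PSEQ score by more than 20 points at 12 weeks after baseline". Under Section 5 the number of successes "will be tested with Fisher's exact test".

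The allocated treatments are short. Section 4.6 gives the drugs for four weeks (for example "Eperisine (3 × 50 mg per day) for four weeks", cited here only for duration), and Section 4.10 places the rESWT sessions at weeks 0 to 3. Section 7.4 allows no other drug treatment for back pain in any arm. Section 4.9 leaves patients and therapists unblinded but blinds the assessor, whose task is to judge treatment success. Section 4.12 says that all assessments, at baseline and in follow-up, "will be performed by assessors blind to the intervention".

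**The concern.** A questionnaire total can be compared between arms only if every item asks every patient the same thing. Item 7 does not. Taken literally, a patient on rESWT alone rates coping without celecoxib and eperisone, because those drugs are outside the allocated regimen. A patient in either C-E arm rates coping without anything beyond those same drugs.

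The parenthesis is naturally read as part of what the patient sees, since the item about work in the same list also carries a parenthesis that explains its meaning. If it is only a note for staff, passing it on to patients would have the same effect.

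At stake is whether part of a between-arm difference in success could come from the question and not from the treatment. A patient close to the 20-point cut-off can be classified differently by a few points on one item. A second, conditional issue is that a form or prompt tailored to the arm would show the allocation to an assessor who is meant to be blind.

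**Working it through.** **1. Which comparisons are exposed.** Set the reference for additional medication side by side:

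| Arm | Drugs that item 7 treats as not additional |
|---|---|
| rESWT plus C-E | celecoxib, eperisone |
| C-E alone | celecoxib, eperisone |
| rESWT alone | none |

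The first two rows agree, so combination versus C-E alone is little affected. The third row differs from both. rESWT alone versus C-E alone is one of the two comparisons that Section 5.1 says the trial can test. Combination versus rESWT alone is described there as pilot information.

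**2. When the asymmetry applies.** Baseline precedes first treatment (Section 4.12; the first-visit heading in Tables 5 and 6 also puts baseline assessment before randomization). At weeks 2 and 4 the drug course is running or just finishing, so the literal meaning differs by arm. At weeks 12 and 24 all allocated treatment is over, and the qualifier has no clear referent in any arm.

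**3. The plan's own figures.** Table 9 (40% vs 70%, two-sided 5%, power 0.8), Fleiss formula:

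n = [1.960·√(2·0.55·0.45) + 0.8416·√(0.4·0.6 + 0.7·0.3)]² / 0.30² = 42

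With continuity correction this becomes 49. Both match. At 50 per arm, normal-approximation power for 35% vs 70% is 95.0%, matching Table 7. (Table 7's caption says 40%, which would give 86.6%. That is a separate point.) The question about item 7 alters none of these figures.

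**4. How far a differential on item 7 could move the result.** Item 7 carries at most 6 of 60 points (10%). It cannot produce a gain above 20 by itself, but it can move patients across the cut-off. The documents give no SD of PSEQ change; I assume normal change with SD σ = 8 to 15. If the success rate without distortion is p and the item shifts one arm by δ points:

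p′ = Φ(Φ⁻¹(p) + δ/σ)

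For p = 0.35, Φ⁻¹(p) = −0.385. With δ = 2 and σ = 8: Φ(−0.385 + 0.250) = 0.446. With δ = 2 and σ = 15: Φ(−0.385 + 0.133) = 0.401.

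The rejection probability is the exact two-sided Fisher test at n = 50 per arm, summed over both binomials. The third column takes a true rate of 35% in both arms. The fourth takes 35% vs 70%, with the shift working against the true difference.

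| δ (points) | 35% becomes | Rejection, no true difference | Power, 35% vs 70% |
|---|---|---|---|
| 0 | 35.0% | 3.0% | 93.1% |
| 1 | 37.5–39.7% | 3.6–5.1% | 84.1–89.0% |
| 2 | 40.1–44.6% | 5.4–12.3% | 69.3–83.3% |
| 3 | 42.6–49.6% | 8.7–25.8% | 50.0–75.9% |

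Ranges run over σ = 15 to 8. Both δ and its sign are assumptions.

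**The case against.** The strongest reply is about timing. Success is judged at week 12, when a compliant patient in any arm takes no study drug and no other back-pain drug is permitted. All arms are then in the same position, and what remains is a possible difference in interpretation. This stands, and it limits the point: the clear asymmetry falls at visits that do not define success.

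The size is also open to challenge. A mean shift of 2 to 3 points is 33–50% of the item's range across a whole arm (2/6 to 3/6), and nothing in the documents supports that figure. This stands too. The full 6 points would require the largest possible shift in every patient; it is a ceiling and not a scenario.

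Three stronger readings are tempting, and the documents do not carry them:

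- *That patients get different questionnaires by arm and by visit.* Only one sentence is printed, naming all three regimens. No arm-specific or visit-specific form is described. The change in meaning over time is inferred from the treatment schedule. Because baseline comes before treatment, such a change starts from the same point in every arm and is not by itself a between-arm bias.
- *That item 7 unmasks the assessor.* The text as printed lists every regimen and so reveals nothing. Unmasking requires an arm-specific form or prompt that the assessor sees, and the mode of administration is not given. Unblinded patients could disclose their arm in any case.
- *That the wording tilts the trial for or against rESWT.* Nothing fixes how patients would apply a qualifier about treatment that ended eight weeks before the endpoint, so no direction can be claimed.

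The reply does not remove the stated wording itself, which defines one component of the primary outcome by allocation.

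**Conclusion.** The point holds in a limited form. One of ten PSEQ items, 6 of 60 points, is defined differently for rESWT alone than for the two C-E arms. This touches the powered comparison of rESWT alone with C-E alone and the pilot comparison of combination with rESWT alone. Combination versus C-E alone is little affected.

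At week 12 any bias depends on how patients interpret the phrase; its direction and size cannot be derived from the documents. Under the assumed normal model with SD 8 to 15, a 1-point differential leaves the false-positive rate near nominal. A differential of 2 to 3 points would be material, taking a 35% success rate to about 40–50%. Disclosure of allocation to the assessor is a possibility only if arm-specific text is used. This is an inexpensive correction to the instrument and not a reason to doubt the design as a whole.

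**What to change.** Use one treatment-neutral wording of item 7, identical in all arms and at all visits including baseline, with the same stated reference for medication throughout. Deleting the parenthesis is not enough: the word 'additional' would still invite patients to read the item against their own drugs, so its arm-relative sense must go as well. Which common reference to adopt is for the sponsor to choose and state. Also state how the form is completed, and keep any arm-identifying text off it and out of any prompt.

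Before enrolment the cost is a line in the protocol and one on the questionnaire; the 49 required and 50 planned per arm are unchanged. If enrolment has begun, document which wording was used, in which arms and at which visits, and add a sensitivity analysis of the nine-item total without item 7. That total runs from 0 to 54, so its cut-off should be fixed in advance: either more than 20 points as now, or the proportional value of more than 18 (20 × 54/60). Section 5 writes the success threshold as 20% where Sections 4.11.1 and 5.1 write 20 points; that must be reconciled first, as a separate matter.

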4.4. Inclusion criteria

- Adults (both male and female) with non-specific low back pain for more than three months.
- Age range: between 18 and 80 years.
- Willingness of the patient to participate in the study, and written informed consent signed and personally dated by the patient.
- Chronic non-specific low back pain clinically diagnosed as repeated lumbar sourness and swelling pain or a chronic progressive process, accompanied by (i) X-ray examination to exclude lumbar vertebrate fractures, spondylolysis, spondylolisthesis and severe osteoporosis, and/or (ii) MRI with normal signal or low nucleus pulposus signal.
- No contraindications for rESWT.

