5.1. Power analysis

In none of the studies on ESWT for non-specific low back pain performed so far (Nedelka et al., 2014; Lee et al., 2014; Han et al., 2014; Moon et al., 2016) a definition of treatment success was defined, a Power analysis was reported and the PSEQ score was used to assess clinical outcome. Accordingly, these studies are only of very limited use for the purpose of performing a Power analysis of the proposed study.

Based on anecdotal evidence from several therapists in Europe and Latin America who have been using rESWT for non-specific low back pain for more than a decade we hypothesize that treatment of chronic non-specific low back pain with rESWT alone as described above will result in a success rate of approximately 70%, and the combination of rESWT and C-E drugs in a success rate of approximately 85%. Furthermore, based on our own experience we hypothesize that treatment of chronic non-specific low back pain with C-E drugs alone as described above will result in a success rate of only approximately 35%

On this basis we performed a Power analysis, both for a percentage of 35% as well as for various other percentages (ranging between 10% and 99.9%) of patients with treatment success when treated with C-E drugs alone, accounting for a two sided-confidence interval of 95% (and, thus, a type-1 error rate of 5%). Calculations were performed using the software Open Source Epidemiologic Statistics for Public Health (www.openepi.com). The results are summarized in Tables 7 and 8.

Table 7. Power for the proposed RCT on rESWT plus C-E drugs or rESWT alone for chronic non-specific low back pain, accounting for a two sided-confidence interval of 95% and a percentage of patients with treatment success of 40% when treated with C-E drugs alone (assuming n=50 patients per group).

Percent of patients treated with rESWT plus C-E drugs or C-E drugs alone with treatment success [%]	Power based on Normal approximation [%]	Power based on Normal approximation with continuity correction [%]
99.9	100	100
90	100	100
85	100	100
80	99.8	99.6
70	95.0	92.4
60	71.3	63.5
50	32.7	25.2
40	7.2	3.5
35	1.1	0

Table 8. Power for the proposed RCT on rESWT plus C-E drugs for chronic non-specific low back pain, accounting for a two sided-confidence interval of 95% and a percentage of patients with treatment success of 70% when treated with rESWT alone (assuming n=50 patients per group).

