In summary, the proposed study has a power of more than 0.8 in finding a difference in treatment success (individual improvement of the PSEG score by more than 20 points at 12 weeks after baseline) between rESWT plus C-E drugs and C-E drugs alone, as well as between rESWT alone and C-E drugs alone, for treating chronic non-specific low back pain when randomizing at least 49 patients into each group.

On the other hand, the proposed study does not have a power of more than 0.8 in finding a difference in treatment success (individual improvement of the PSEG score by more than 20 points at 12 weeks after baseline) between rESWT plus C-E drugs and rESWT alone, for treating chronic non-specific low back pain when randomizing less than 134 patients into each group.

In summary, the proposed study can test the following hypotheses in the treatment of chronic non-specific low back pain: (i) rESWT plus C-E drugs is superior to C-E drugs alone, and (ii) rESWT alone is superior to C-E drugs alone. Furthermore, the proposed study can retrieve important pilot data for designing a follow-up study testing the hypothesis that rESWT plus C-E drugs is superior to rESWT alone in the treatment of chronic non-specific low back pain.

Collectively, the results of the Power analysis reinforce the validity of the proposed study protocol for testing efficacy and safety of rESWT using the Swiss DolorClast for chronic non-specific low back pain.

6. Patient protection procedures

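### A success threshold above 20 points on a 0–60 PSEQ, with no baseline PSEQ limit at entry, makes every patient who starts at 40 or higher a certain failure in all arms

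*Combined protocol and SAP*

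**What the plan says.** Section 4.11.1 makes the PSEQ the primary outcome. It gives the scale as "Scores on the PSEQ may range from 0 to 60, with higher scores indicating stronger self-efficacy beliefs" and defines the responder endpoint: "treatment success is defined as individual improvement of the PSEQ score by more than 20 points at 12 weeks after baseline". The same section puts the minimal clinically important difference at 11 points. The conclusion of Section 5.1 repeats the points threshold (with the scale's acronym misspelt): "individual improvement of the PSEG score by more than 20 points at 12 weeks after baseline". Section 5, where Fisher's exact test is assigned to this endpoint, has a different unit: "individual improvement of PSEQ score by more than 20% at 12 weeks after baseline".

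Section 4.4 opens with "Adults (both male and female) with non-specific low back pain for more than three months" and goes on to age, consent, diagnosis with imaging, and contraindications. Section 4.5 adds medical exclusions. Neither sets a limit on PSEQ or a minimum for pain or disability. The NRS bands in Section 4.6 govern drug dosing only. Section 4.7 offers entry to everyone who meets these criteria.

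Section 5.1 assumes success in about 70% on rESWT alone and about 35% on C-E drugs, and "the combination of rESWT and C-E drugs in a success rate of approximately 85"%. These rates come from anecdotal evidence and the investigators' own experience. No baseline PSEQ distribution is given. Table 9, which supports the minimum of 49 per group, uses 40% for C-E drugs instead of 35%.

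**The concern.** A responder threshold on a bounded scale works only for patients with enough room below the top. Here that room is never checked. Anyone who enters at 40 or above is a non-responder before treatment starts, whatever the arm. Patients entering between 40 and 49 could gain 11 points or more, which the protocol itself regards as worthwhile, and would still count as failures.

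Such patients add only failures. If the planned rates were meant for patients able to succeed, the observed rates in all arms shrink by the same factor, absolute differences narrow and power falls. The ceiling also limits the rates that can be reached: 85% is out of reach if more than 15% of the combination arm starts at 40 or above, and 70% is out of reach if more than 30% of the rESWT arm does. Section 5.1 makes no visible allowance for this.

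**Working it through.** **Inputs.** Scale maximum 60 and threshold above 20 points (Section 4.11.1); 50 per arm (Section 4.9); two-sided 5% level (Section 5.1); success rates 70%, 85% and 35% (Section 5.1 text) and 40% for C-E drugs (Table 9). The share *f* of patients at or above the ceiling is not in the documents and is varied as an assumption.

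**Where the ceiling starts.** The largest possible gain is 60 − baseline.
- Points wording: success needs 60 − b > 20. At b = 39 the largest gain is 21, so success is possible. At b = 40 it is 20, which is not above 20. The ceiling starts at 40.
- Percentage wording, read as percent of baseline: success needs 60 > 1.2b. At b = 50, 1.2 × 50 = 60, so success is impossible. The ceiling starts at 50.

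**Reproducing the plan's figures.** With p̄ = (p1 + p2)/2, SE0 = √[2p̄(1 − p̄)/n] and SE1 = √[(p1(1 − p1) + p2(1 − p2))/n], power = Φ[(p1 − p2 − 1.96·SE0)/SE1]. The continuity-corrected version subtracts 1/n from the difference.
- 70% vs 35%, n = 50: SE0 = 0.0999, SE1 = 0.0935, z = (0.35 − 0.1958)/0.0935 = 1.65, power 95.0% (92.4% corrected). This matches the 70% row of Table 7. That table is captioned 40%, but its values correspond to 35%.
- 70% vs 40%: power 86.6%. The continuity-corrected Fleiss sample size is 49, as in Table 9.

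**Effect of the ceiling if the planned rates hold only below it.** Each rate becomes p(1 − f). For example, at f = 10%, 70% vs 40% becomes 63% vs 36%: SE0 = 0.1000, SE1 = 0.0963, z = (0.27 − 0.1960)/0.0963 = 0.77, power 77.9%.

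Power for rESWT alone vs C-E drugs at 50 per arm, normal approximation, with Fisher's exact test (the planned test) in brackets:

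| Share *f* | 70% vs 35% | 70% vs 40% |
|---|---|---|
| 0 | 95.0% (93.1%) | 86.6% (82.9%) |
| 5% | 92.6% (90.2%) | 82.4% (78.4%) |
| 10% | 89.6% (86.6%) | 77.9% (73.5%) |
| 20% | 82.0% (77.2%) | 68.1% (62.5%) |
| 30% | 72.6% (65.8%) | 58.0% (50.8%) |

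On the Table 9 rates, the continuity-corrected requirement rises from 49 per arm to 60, 75 and 93 at shares of 10%, 20% and 30%.

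Combination vs C-E drugs at f = 30%: 95.5% for 85% vs 35%; 90.0% for 85% vs 40% (Fisher 86.8%).

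**How large could *f* be?** For illustration only, take a normal baseline distribution with SD 10 to 12 and f = 1 − Φ[(39.5 − mean)/SD]. This gives about 3–5% at mean 20, 7–11% at 25, 17–21% at 30 and 33–35% at 35. Nothing in the documents favours one of these means.

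**The case against.** The arithmetic of the ceiling is not in dispute. The case against giving it much weight has five parts.

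- **The definition is unsettled.** If the percentage wording in Section 5 is the intended one, an entry limit of 39 would turn away patients at 40 to 49 who can succeed. This stands: the definition has to be settled before any limit is written.
- **The power loss is conditional.** A reader might infer that the planned rates describe only patients able to succeed, and hence that the trial is underpowered. The documents do not say so. Section 5.1 applies the rates to treatment of the condition in general. If they already cover everyone enrolled, the ceiling is inside them and no planned power is lost. This stands too, although Section 5.1 does not say that the ceiling was considered.
- **The size is unknown.** At an assumed mean of 20 the share is only 3–5%. This stands; the table above shows what different shares would imply and does not estimate the actual loss.
- **There is no bias.** A reader might also infer that fixed failures distort the comparison. Randomisation balances them in expectation, they do not inflate the type I error, and under the dilution model the ratio of success rates is unchanged (56/28 = 70/35). Only the absolute difference and the power shrink.
- **An entry limit is not free and is not a full cure.** If a third of candidates were excluded, filling 150 places would take roughly 224 to 231 otherwise eligible patients (150/0.67 to 150/0.65), and the sample would represent the source population that Section 4.7 aims for less well. A patient at 39 would still need a perfect 60. This stands as a cost to be weighed.

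**Conclusion.** On the points definition in Sections 4.11.1 and 5.1, a patient entering with a PSEQ of 40 or more cannot be a treatment success, and the eligibility criteria let such patients in. This follows from the protocol's own numbers. On the percentage wording in Section 5 the same problem begins at 50.

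The consequence for power depends on two things that the documents do not give: the share of patients at the ceiling, and whether the planned rates exclude them. If they do exclude them, the exposed comparison is rESWT alone vs C-E drugs. For 70% vs 35% it keeps more than 0.8 power up to a 20% share by the normal approximation, though not by Fisher's test. For 70% vs 40% it drops below 0.8 at a 10% share by the normal approximation and already at 5% by Fisher's test. The combination vs C-E drugs remains above 85% for shares up to 30%. The combination vs rESWT alone is already acknowledged in Section 5.1 as underpowered.

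This is a possible loss of efficiency and no threat to validity. It merits a cheap improvement and falls short of a mandatory correction.

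**What to change.** 1. Reconcile Sections 4.11.1, 5 and 5.1 on one success definition, in points or in percent.
2. If the points definition stands and recruitment has not begun, add to Section 4.4 that the baseline PSEQ must be 39 or less, and state in Sections 4.9 and 4.10 that it is scored before the allocation envelope is opened. Section 4.11.1 already has the PSEQ collected at baseline, so no new measurement is needed.
3. If recruitment has begun, keep every randomised patient in the intention-to-treat analysis, report the number per arm at or above the ceiling, and prespecify a supportive success analysis in patients below it. Prespecifying it respects the bar on unplanned subgroup analyses in Section 5.

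The cost of step 2 is slower recruitment, in proportion to the share excluded, and a conclusion limited to patients with lower self-efficacy at entry. Step 3 costs a few lines of text and one extra table.
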